**G. Summarize Knowledge to be Gained:**

Successful completion of this study (additional aims evaluated outside of the CTRC and UCD) will clarify whether the changes in the GH/IGF-I-axis among HIV+ persons are expected age-related GH changes, or represent a unique pathway. For the exercise intervention specifically:

1. If HIV+ have less improvement in chair rise compared to HIV-, we have confirmed that something is interfering with the ability to respond appropriately to a similar exercise intervention (IGF-I, testosterone, inflammation, nutrition, etc).
2. If HIV+ have similar response in chair rise time, then there may be no issues with response to exercise, however this would be in contrast to prior studies in younger adults. Peak V02 and 1-RM differences between groups will also be evaluated to ensure this is not a sensitivity limitation of chair rise vs more intensive measures.
3. If only the HIV+ high-intensity group have improvement in chair rise, this supports that future interventions should target higher-intensity exercise rather than simply lifestyle modifications if improvement in function is the intended outcome. If the HIV+ high-intensity group has improvement in chair rise, but this is associated with greater sedentary time and less improvement on other measures (sleep, mood, exercise efficacy, etc), this raises concerns regarding the long-term durability and compliance with an exercise intervention of this intensity.
4. If #1, then we will look at measures that may interfere with the exercise response including
  - a. Systemic IGF-1. Based on our findings and published results from HIV- interventions, we expect that systemic IGF-1 will be lower in the HIV+ group and have less change in an intervention than the HIV- group. However, due to changes in visceral fat which tends to be more pronounced in HIV+ persons with similar BMI, we may see a greater change in IGF-1 in HIV+ vs HIV. This will then be compared to the changes that occur at the level of the muscle, thought to mediate the majority of GH/IGF-I effects on strength and function
  - b. If IGF-I increases in HIV+ but not to the extent seen in HIV-, this confirms our hypothesis. Future studies can investigate whether certain exercise (higher intensity or more intensive REx can result in a greater improvement in function, mediated by a greater increase in IGF-I.

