## C. Study Design and Research Methods

Potentially eligible subjects will be screened during routine clinic visits or over the telephone. Potentially eligible and interested subjects will return for informed consent and a screening/baseline visit. No research procedures will occur prior to consent, including the MOCA.

After obtaining informed consent, participants will undergo a graded exercise test to screen for potential underlying cardiovascular disease. V02 peak will be measured at this time to develop the exercise prescription. All participants will begin with a low intensity lead-in for 1-2 weeks, then advance to a moderate intensity exercise during first 12 weeks. Randomization to continue on moderate versus advance to high intensity will occur at week 13.

**1. Consent & baseline visit.** After obtaining consent, the participant will be evaluated

-After obtaining consent, the participant will be evaluated by

- medical history, physical examination including vital signs
- Montreal Cognitive Assessment (MOCA)
- Resting BP, 12-lead resting ECG, and then a graded exercise test (GXT) administered by research personnel and a clinician experienced in exercise stress testing of older adults ([name]) to screen out volunteers with evidence of ischemic heart disease, serious arrhythmias, or abnormal HR/BP responses to exercise. Briefly, the test will begin at a comfortable walking speed and 0% elevation; speed will be maintained and the grade increased by 2% every 2 min, until the participant reaches 85% of age-predicted maximal heart rate or the test is otherwise terminated. The absolute and relative indicators for terminating an exercise test that are recommended by the American College of Sports Medicine (ACSM) will be employed.
- Baseline physical function assessments will be administered.

**2. Procedure visit #1 (within 14 days of visit #1).** All participants will arrive between 7:30-8am for:

- DXA scan
- Vital signs
- Anthropometrics (waist/hip circumference)
- Blood draw (fasting)
- 36 (up to 46, if needed to ensure 36 paired biopsy samples) volunteer participants (18 HIV+/18 HIV-) will have a muscle biopsy
  - If muscle biopsy at the end of the study cannot be done (patient refuses, change in medications, etc), then the number of biopsies will increase to a maximum of 46 in order to ensure each group has at least 18 paired (entry/completion) biopsy samples.
- Questionnaires

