**2. Exercise testing and training:** All exercise intervention components will include 3 to 4 weekly, supervised sessions of combined CEx + REx at the University of Colorado-Denver (UCD) Exercise Research Laboratory (ERL). All participants will begin with a 2-week supervised, low-intensity exercise acclimation with an experienced research assistant. The initial goal will be to walk on a treadmill for 20-30 continuous minutes at low-intensity (30-40% of maximal aerobic power [VO2max]) and complete 3 sets of 8 repetitions at low-intensity (40-50% of the one-repetition maximum; 1-RM) 3 or 4 days/week. This will facilitate comfort with study equipment and minimize injury.

At 2 weeks, all participants will complete an additional 10 weeks of moderate- intensity exercise, with a goal of 50 minutes of cardiovascular + 3 sets of 8 resistance exercises by the end of the 12 week initial intervention. This will ensure that every participant meets at least the DHHS-PA recommendations in a supervised setting. At week 13, participants will be randomized to continue moderate intensity exercise, or progress to a high-intensity intervention for an additional 12 weeks.

*Maximal aerobic power (VO2 max).* The measurement of VO2max (or peak) will be used to formulate the prescription for CEx at the screening visit. Increases in VO2max in response to exercise training will also verify that the exercise was of sufficient intensity to induce cardiorespiratory adaptations. During an initial 5-min warm-up, walking speed will be adjusted to elicit a HR that is ~70% of maximal HR (from the screening GXT). Speed will then be held constant and the grade of the treadmill will be increased by 2% every 2 minutes until volitional exhaustion or until the test is stopped (see section 4.1.2b). The O2 and CO2 content of expired air will be measured continuously by open circuit spirometry and averaged every 30 sec using an automated online system (TrueMax 2400; ParvoMedics, Sandy, UT). Objective evidence that VO2max has been attained will include at least 2 of the following: a plateau in VO2 despite an increased energy demand, a respiratory exchange ratio in excess of 1.10, and a maximal HR within 10 beats of the age-predicted value. In the absence of these benchmarks, the maximum measured VO2 will be deemed VO2 peak.

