*Muscle strength (1-RM).* Muscle strength will be evaluated as the 1-RM (the maximal weight that can be lifted only 1 time using correct lifting form through the full range of motion) for the upper and lower body REx performed during weeks 1-20. 1RMs will be measured at week 0 and every 4 weeks to week 20. The change in muscle strength from week 0 to 20 will be a secondary outcome measure.

*Exercise intervention.* CEx duration will be increased to 50 minutes of treadmill walking/jogging and exercise intensity will be gradually increased to either 40-50% VO2max (moderate intensity) or 60-70% VO2max (high intensity). By completing 50 minutes of CEx within the 3 weekly visits, we will ensure that all subjects comply with the DHHS guidelines, regardless of their physical activity outside of the routine visits. REx intensity will increase every 2-3 weeks to a target of 3 sets of 8 repetitions at 60-70% of 1-RM (moderate intensity) or >80% of the 1-RM (high intensity).

*Supervised exercise sessions.* Each session will begin with CEx and proceed to REx. Three sets of resistance exercises will include leg press, knee extension, knee flexion, lunges (forward and side), lateral pulldown, chest press, seated row, and dips on a weight-assisted machine. Weight-stack and free weight equipment will be used. Stretching for 10 minutes will conclude each session. Research assistants will supervise exercise, interact frequently with participants, and encourage feedback regarding any discomforts or undue fatigue experienced during or after the exercise sessions. The individualized exercise prescriptions will be geared toward increasing the exercise stimulus while avoiding unfavorable events.

*Physical activity recommendations outside of supervised sessions.* Each participant will be provided with a pedometer (Omron) and recommendations to achieve at least 5,000 steps/day. Walking paths near the participants' home will be mapped for each participant. Information from the NIH Healthy Aging site (exercises for the older adults, nutrition advice, etc) will be provided to each participant at study entry and tip sheets for ways to decrease sedentary time will be provided. Participants will be encouraged to utilize fitness apps (MyFitnessPal, etc) and each subject will receive instructions to partake in physical activity "most" days of the week, outside of their 3x/week supervised sessions.

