## **F. Data Analysis Plan:**

### **Statistical Considerations**

Sample Size Calculations: The primary outcome for sample size calculations is change from baseline in chair rise pace. We assume a change from baseline of 1.5 (SD=1.54) seconds or larger, based on differences observed by fall history [85]: Sample sizes of 36/group will yield an estimate of 29 patients per group at week 16 (~20% dropout). 29 subjects per group achieves over 80% power to detect a between group difference of 1.5 seconds with a significance level of 0.05 and the standard deviation conservatively estimated at 2.0 seconds[110] using a two-sided two-sample equal variance t-test.

Matching and Randomization: Enrollment in the uninfected arm will be constrained to lag behind HIV-enrollments. Upon the enrollment of every 5th HIV-infected patient, HIV-uninfected enrollment will be evaluated and recruiting goals updated to ensure a similar age (<60; >=60), gender, BMI, and smoking

distribution. Given the smaller proportion of women in the HIV-infected population, we plan to enroll fewer women. The randomization will be blocked by gender and exercise intensity to ensure balance according to the following scheme:

Exercise Intensity	Moderate (N=36)		High (N=36)	
HIV-Infected (N=36)	Men:	15	Men:	15
	Women:	3	Women:	3
Controls (N=36)	Men:	15	Men:	15
	Women:	3	Women:	3

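### Section G, item 3 names lifestyle modification as the alternative to high intensity, but the trial directly compares high intensity only with continued moderate supervised exercise

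*Combined protocol and SAP*

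**What the plan says.** Section G of the combined protocol and SAP sets out how possible results would be read. Item 3 begins with a condition, "If only the HIV+ high-intensity group have improvement in chair rise", and concludes that future interventions "should target higher-intensity exercise rather than simply lifestyle modifications if improvement in function is the intended outcome".

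The design is described in three places:

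- Section C: "Randomization to continue on moderate versus advance to high intensity will occur at week 13".
- Section D, item 2 (Exercise testing and training): "All exercise intervention components will include 3 to 4 weekly, supervised sessions of combined CEx + REx". On the first phase: "At 2 weeks, all participants will complete an additional 10 weeks of moderate- intensity exercise". On the second: "At week 13, participants will be randomized to continue moderate intensity exercise, or progress to a high-intensity intervention for an additional 12 weeks".
- Section F (Matching and Randomization): "The randomization will be blocked by gender and exercise intensity to ensure balance according to the following scheme". The table that follows has two intensity levels of 36 each, split equally by HIV status.

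Section D, item 2 also describes advice for the time between sessions. Each participant receives a pedometer and "recommendations to achieve at least 5,000 steps/day", with mapped walking routes, material on healthy ageing, tips for sitting less, encouragement to use fitness apps, and an instruction to be active on most days. None of this is assigned by arm.

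**The concern.** Item 3 recommends one approach over another, and the alternative it names is not an arm of the trial. Someone interpreting the results by section G would take a favourable high-intensity result as support for high intensity over lifestyle modification. The treatment actually compared, supervised moderate training, would drop out of the conclusion. The Background and section IV.A both look ahead to exercise recommendations for older adults with HIV, so the identity of the comparator matters.

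The trigger for the conclusion is also weak. Improvement in one group and not in another does not show that the two groups differ. The randomised evidence on intensity is the difference between arms.

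**Working it through.** The point turns on what each arm receives, so the main check sets the sections side by side. A short calculation follows for the size of the relevant cells.

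**Step 1: what differs between arms** (section D, item 2, with section C for timing)

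| Component | Moderate arm | High arm |
|---|---|---|
| Weeks 1–2 | Supervised, low intensity | Same |
| Next 10 weeks | Supervised, moderate intensity | Same |
| From week 13, for 12 weeks | Supervised: 40–50% VO2max, 60–70% of 1-RM | Supervised: 60–70% VO2max, >80% of 1-RM |
| Supervised sessions per week | 3 to 4 | 3 to 4 |
| Step target, walking routes, tip sheets, activity advice | Yes | Yes |

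Only the third row differs. The advice is common to both columns, so the randomised contrast does not measure its effect. A moderate-arm participant is planned to attend at least 24 × 3 = 72 supervised sessions, which is not lifestyle modification alone.

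**Step 2: who could supply the comparator in item 3**

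The allocation table accounts for 36 + 36 = 72 participants, all in supervised exercise. The number allocated to advice without supervised exercise is 0. The shared first 12 weeks do not supply the comparison either, because everyone is exercising then.

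**Step 3: size of the contrast that item 3 can use**

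Item 3 concerns HIV+ participants. The table plans 15 men + 3 women = 18 per intensity level, so the contrast is 18 against 18.

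Inputs from section F: difference 1.5 s, SD 2.0 s, two-sided 0.05, two-sample t-test, about 20% dropout. The noncentrality is (1.5/2.0) × √(n/2), with 2n − 2 degrees of freedom.

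- Plan's own figure: 36 × 0.8 = 28.8, about 29 per group. Noncentrality 0.75 × √14.5 = 2.86; power 0.801. The plan's claim of over 80% is reproduced.
- 18 per cell: 0.75 × √9 = 2.25; power 0.59.
- After 20% dropout: 18 × 0.8 = 14.4, so 14 to 15 per cell. Noncentrality 1.98 to 2.05; power 0.48 to 0.51.

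The last two lines assume that the section F difference and SD carry over to the intensity contrast among HIV+ participants. They are single-time-point figures; section F expects the repeated chair-rise measurements to add power. They describe a comparison between cells, not the chance of detecting improvement within one cell. Their use here is to show that these are small cells, in which an absence of apparent improvement is weak evidence of no effect.

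**The case against.** Three arguments can be made for leaving the sentence alone.

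**An indirect inference is available.** Item 3 applies only if the HIV+ high-intensity group alone improves. HIV+ participants given supervised moderate exercise plus all the advice would then not have improved, so advice without the exercise would presumably not suffice either. This is reasonable as far as it goes. It needs the unstated assumption that adding moderate exercise does not cancel a benefit of the advice. It also treats non-improvement in one cell of 18, or 14 to 15 after dropout, as absence of effect. Even if granted, it does not estimate high intensity against lifestyle modification. What stands is that a reader should not conclude that the trial is wholly uninformative about lifestyle modification. The accurate statement is that it gives no direct estimate.

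**The term may be shorthand.** The documents do not define lifestyle modifications, and the moderate programme is built to meet public guideline levels, so the moderate arm may be what was meant. That reading is possible. It would still leave item 3 mislabelling a supervised laboratory programme. The Background mentions exercise and lifestyle modification as alternatives, and Hypothesis 1b names the intensity contrast correctly as high against moderate.

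**Nothing operational depends on it.** This stands in full. Hypothesis 1b, the fourth objective in section IV.A, the randomisation and the analysis plan all work with moderate and high intensity. No test, sample size or reporting rule uses a lifestyle comparator.

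**Conclusion.** The point holds as a fault of interpretation confined to one conditional sentence. Item 3 names a comparator to which 0 of 72 planned participants are allocated. The trial's direct evidence on intensity among HIV+ participants is high against continued moderate supervised exercise from week 13, planned at 18 against 18. The table gives planned numbers; section C randomises those still on study at week 13, so the randomised cells could be smaller.

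A reader might infer that the design is defective or needs a lifestyle arm. The documents do not support that: the stated intensity hypothesis is high against moderate, and the design matches it. A reader might also infer that a favourable result will be reported as evidence against lifestyle advice. No section sets such a reporting rule; item 3 only invites that reading.

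The conclusion rests on the descriptions of the arms and of the advice, and on no numerical assumption. The power figures bear only on how much weight the indirect inference can carry.

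**What to change.** Reword item 3 along these lines: *If, among HIV+ participants, the between-arm difference in chair-rise change favours high intensity, this supports higher-intensity over continued moderate-intensity supervised cardiovascular and resistance exercise, after the shared initial 12 weeks (low-intensity lead-in, then moderate).*

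Then either delete the lifestyle comparator or add that the study does not directly test lifestyle modification without supervised exercise. Changing the trigger matters as much as changing the comparator. If item 3 still depended on only one group improving, it would infer a difference between intensities without comparing them.

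The cost is a sentence or two in section G and a narrower stated conclusion. Design, data collection, sample size and primary analysis stay as they are.
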